6.2 IMPORTANT PROTOCOL VIOLATIONS

Important protocol violations (IPV) affecting subjects' rights will be identified separately from those affecting analysis sets in the study report. Patients with important PVs that could potentially impact efficacy endpoints will be excluded from the PPS (Refer to [Section 6.3](#)).

The protocol violations are listed in the [Table 6.2: 1](#) below. They will be reviewed at Medical Quality Review Meetings (MQRMs) conducted periodically based on data accumulated during the trial. A list of protocol deviations will be discussed at the blinded report planning meeting (BRPM).

If the data show other important PVs, this table will be supplemented accordingly at MQRMs or BRPMs or through team review of the manual PV log. The decision whether a patient will be excluded from the analysis will be made at the final BRPM prior to DBL.

Proprietary confidential information © 2017 Boehringer Ingelheim International GmbH or one or more of its affiliated companies

Table 6.2: 1 important protocol violations

Category /Code	Description	Example/Comment	Excluded from PPS	Automatic /Manual
A	Entrance criteria not met			
A1	Inclusion criteria not met			
A1.1	Patient younger than 55 years of age	Inclusion criteria 1 not met as specified in the protocol.	Yes	Automatic
A1.2	No confirmed diagnosis of prodromal AD on neuropsychological testing	Inclusion criteria 3 not met as specified in the protocol.	Yes	Automatic
A1.3	No confirmation of abnormal markers of AD pathology	Inclusion criteria 4 not met as specified in the protocol.	Yes	Automatic
A1.4	Received drugs for treatment of AD within three months of screening	Inclusion criteria 5 not met as specified in the protocol.	Yes	Automatic
A1.5	Inadequate education and language	Inclusion criteria 6 not met as specified in the protocol.	Yes	Automatic
A1.6	Inadequate study partner reliability	Inclusion criteria 8 not met as specified in the protocol.	Yes	Automatic
A2	Exclusion criteria met			
A2.1	Mild cognitive impairment	Exclusion criteria 1 met as specified in the protocol.	Yes	Automatic
A2.2	Substantial concomitant cerebrovascular disease	Exclusion criteria 2 met as specified in the protocol.	Yes	Automatic
A2.3	Symptomatic and unstable/uncontrolled conditions	Exclusion criteria 4 met as specified in the protocol.	Yes	Automatic
A2.4	Any other psychiatric disorder	Exclusion criteria 6 met as specified in the protocol.	Yes	Automatic
A2.5	Any suicidal behavior in the past 2 years	Exclusion criteria 7 met as specified in the protocol.	No	Automatic
A2.6	Any suicidal ideation of type 4 or 5 in the C-SSRS in the past 3 months	Exclusion criteria 8 met as specified in the protocol.	No	Automatic
A2.7	Participation in AD study less than 3 months from screening, treatment for disease modification or non-prescription medications	Exclusion criteria 9 met as specified in the protocol.	Yes	Automatic
A2.8	Known history of HIV infection	Exclusion criteria 11 met as specified in the protocol.	Yes	Automatic

Proprietary confidential information © 2017 Boehringer Ingelheim International GmbH or one or more of its affiliated companies

Table 6.2: 1 (continued) important protocol violations

Category /Code	Description	Example/Comment	Excluded from PPS	Automatic/ Manual
A2	Exclusion criteria met			
A2.9	Prohibited drugs within 3 months prior to study participation	Exclusion criteria 16 met as specified in the protocol.	Yes	Automatic
A2.10	Uncompensated hearing loss	Exclusion criteria 20 met as specified in the protocol.	Yes	Automatic
B	Informed consent not available/not done			
B1	Informed consent not available/not done	Informed consent date missing; no signature on ICF	Exclude from All	Automatic /Manual
B2	Informed consent too late	
Check if informed consent date (actual consent date) was prior or on Visit 1.
 
Applicable to all informed consents. Date of informed consent was after the date of any study-related procedure.
 
If patient signed the wrong version of ICF and then signed the correct version of ICF with the date after screening, it is still deemed as IPV
	No	Automatic /Manual
C	Trial medication and randomization			
C1	Incorrect trial medication taken			
C1.1	Incorrect trial medication taken during study	
Any deviation. Check whether the medication packages dispensed (med. Numbers entered into RDC) has the correct content (to be seen from the med. number list that was the basis for packaging). If content was correct, the deviation will only be noted. Otherwise, the cases will be described individually and possibly excluded.
 
In addition, check whether the dispensed packages match the randomized treatment of the patient (IVRS assignment). If not, and if treated consistently throughout the trial, analyze as treated.
	Yes	Automatic

Proprietary confidential information © 2017 Boehringer Ingelheim International GmbH or one or more of its affiliated companies

Table 6.2: 1 (continued) important protocol violations

Category /Code	Description	Example/Comment	Excluded from PPS	Automatic /Manual
C2	Randomisation order not followed			
C2.1	Error by the vendor who implemented the randomization scheme	
E.g., the same randomization number was given to different patients or the assignment of duplicate medication numbers or incorrect medication numbers.
 
Verify by comparing the medication numbers and randomization numbers from IVRS.
 
If a patient actually receives the correct medication despite the wrong kit, they will not be excluded from the PPS.
 
Vendor to check before unblinding.
	Yes	Manual
C3	Non-compliance with study medication			
C3.1	Non-compliance with study medication	Compliance < 80% or >120 %	Yes if <80%	Automatic /Manual
D	Concomitant medication			
D1	Prohibited medication use before the treatment period of the trial	To be determined on a case by case basis.	Yes	Automatic /Manual
D2	Prohibited medication use during the conduct of the trial	To be determined on a case by case basis.	Yes	Automatic /Manual
E	Trial specific protocol violations			
E1	Negative pregnancy test result not obtained during the study participation		No	Automatic
E2	Treatment not discontinued due to HR elevation as described in CTP section 3.3.4.		No	Automatic
E3	Study partner change during study.		Yes	Automatic
E4	Assessments administered by unqualified rater		Yes	Manual
E5	C-SSRS not administered at every visit		No	Automatic

Proprietary confidential information © 2017 Boehringer Ingelheim International GmbH or one or more of its affiliated companies

Table 6.2: 1 (continued) important protocol violations

Category /Code	Description	Example/Comment	Excluded from PPS	Automatic/Manual
F	Incorrect timing of endpoint measurements			
F1	Incorrect timing - assessments			
F1.1	Assessment order not followed	NTB not administered in order specified in CTP	Yes	Automatic
F1.2	Rater switch on primary endpoint	NTB not administered by same rater	Yes	Manual
F2	Incorrect timing – times of measurements			
F2.1	Assessment of NTB outside of window between visits	NTB assessment time >2 hour from Visit 3 NTB assessment time.	Yes	Automatic

KEY: PPS – Per Protocol Set

6.3 PATIENT SETS ANALYSED

SCR - Screened set: All patients screened for the trial, with informed consent given and who completed at least one screening procedure at Visit 1.

RS- Randomized set: This patient set includes all patients who signed the informed consent form and were also randomized, regardless whether the patient was treated with trial medication or not.

TS-Treated set: All patients who were randomized and treated with at least one dose of study drug.

FAS- Full analysis set: The full analysis set (FAS) will consist of all randomized patients who were treated with at least one dose of study drug and had a baseline and at least one post baseline on treatment primary endpoint NTB assessment (or secondary endpoint assessment). The FAS will be used for the primary analyses (and secondary analyses).

PPS- Per protocol set: All patients in the FAS without important protocol deviations that impact efficacy assessments. No analyses for the CTR are planned using the PPS set.

The SCR, RS and TS will be used to populate patient disposition and the TS will be used for demographics, baseline characteristics, treatment exposure, and safety analyses (including adverse events, laboratory measurements, vital signs, and ECG). Safety analyses will assign patients to the treatment group based on the treatment received.

If a patient erroneously receives the wrong dose of study drug, the patient's efficacy data will be analyzed in the randomized treatment group and the patient's safety data will be analyzed in the actual treatment group.

The efficacy analyses will follow the intention-to-treat (ITT) principle in assigning patients to treatment groups. I.e., efficacy analyses will be analyzed as randomized using the FAS.

If a patient receives a different study drug than randomized, this will be noted as an IPV.

Proprietary confidential information © 2017 Boehringer Ingelheim International GmbH or one or more of its affiliated companies

Table 6.3: 1

Patient sets analyzed

Class of endpoint	Patient set		
	SCR	RS	TS
Primary			OC
Secondary			OC
Further			OC
Safety endpoints			OR
Disposition	OR ¹	OR ¹	OR ¹
Demographic		OR ²	OR
Baseline endpoints		OC	
Disclosure tables	OR		OR

1) Disposition table requires multiple patient sets to populate

2) Additional table for clinical trial disclosure requirements

Note: For definitions of OC (Observed Case) or OR (Original Results) refer to Section 6.6.

Note that the number of patients with available data for an endpoint may differ. For details, see Section 6.6.

6.5 POOLING OF CENTRES

This section is not applicable because centre/country is not included in the statistical model.

6.6 HANDLING OF MISSING DATA AND OUTLIERS

Original result (OR) analysis

Original result analysis implies the analysis of data exactly as observed. OR analysis will be performed on endpoints that are not meaningful to apply any imputation rule on them for replacing the missing values.

6.6.1 Missing efficacy data

NTB

Details on scoring with missing items are described in [section 9.1](#).

ADAS-Cog11

If a patient has 3 or fewer missing ADAS-Cog/11 items, the following algorithm will be used to compute the ADAS-Cog/11 total score:

Total score = [(total score from completed items) / (maximum total score for completed items)]*(maximum total score[=70] for all items in the scale)

Proprietary confidential information © 2017 Boehringer Ingelheim International GmbH or one or more of its affiliated companies

If there are more than 3 missing ADAS-Cog/11 items, ADAS-Cog/11 score will be considered missing at that time point.

ADCS-ADL-MCI

For ADCS-ADL-MCI, if <30% of the items are missing, the total score will be imputed. The sum of the nonmissing items will be prorated to the sum of total items. The imputed number will be rounded up to the nearest integer. If the nearest integer is greater than the maximum possible score, the imputed score will be equal to the maximum score. If >30% of the items are missing, the total score at that visit will be considered missing. For e.g Total score = [(total score from completed items) / (maximum total score for completed items)]*(maximum total score[=69] for all items in the scale)

Supplementary material for [\[8\]](#).

CDR-SB

If only 1 box (of 6) of the CDR is missing, the sum of the boxes will be imputed by prorating the sum from the other 5 boxes. If the score from more than 1 box is not available, the CDR-SB at that visit will be considered missing. For e.g Total score = [(total score from completed items) / (maximum total score for completed items)]*(maximum total score[=18] for all items in the scale) Supplementary material for [\[16\]](#).

Observed cases (OC) analysis

For all efficacy endpoints using MMRM analyses, it is planned to analyze only the available data that were observed while patients were on treatment, i.e., excluding the missing data. In other words, OC analysis will be performed and missing data in this analysis will not be replaced.

The following imputation methods will be used if the rate of missing data is greater than 5%.

The method below will be used for the endpoints using ANCOVA analyses.

Last observation carried forward (LOCF) analysis

The last observation on-treatment need not necessarily be a value selected as a visit value if multiple measurements were performed within a time window for a visit. In this case the last on-treatment value within the time window will be carried forward, while the visit value can be the value that was observed closest to the planned visit date or the first value observed in the time window. See [Table 6.7: 2](#) for further details.

Baseline Observation Carried Forward (BOCF)

As part of the LOCF technique, baseline values will be carried forward if no post-baseline value is available.

6.6.2 Missing safety data and other data

In general, missing data will not be imputed and only observed values will be analyzed. Data of patients who withdrew after the screening examination or were not treated will be only listed.

Proprietary confidential information © 2017 Boehringer Ingelheim International GmbH or one or more of its affiliated companies

6.6.3 Missing AE dates and times

Missing or incomplete AE dates are imputed according to BI standards (see “Handling of missing and incomplete AE dates”) (2).

6.6.4 Missing plasma concentrations and pharmacokinetic parameters

Missing data and outliers of PK data are handled according to (1).

6.7 BASELINE, TIME WINDOWS, AND CALCULATED VISITS

For efficacy, the baseline is defined as the pre-treatment observation at Visit 3. All other baseline variables will be observed from Visit 1.

For laboratory safety measurements, the last values prior to study drug administration will be considered as baseline values.

The midpoint between two on-treatment visits defines the end of a time window, with the midpoint being included in the time window of the preceding visit.

Table 6.7: 1 Time windows for all pre/on-treatment safety visits

Visit number	Visit label	Planned days	Interval (actual days on treatment)
1	Screening	-28	(-∞, PBORI-1]
2	Placebo Run-in period	-14	[PBORI ,TREATMENT-1]
3	Baseline	1	[NA, 1]
4a	Week 1	8	[2, 11]
4b	Week 2	15	[12, 18]
4c	Week 3	22	[19, 25]
5	Week 4	29	[26, 43]
6	Week 8	57	[44, 73]
EOT	Week 12	85	[74, 99]
FU	Follow-up	113	[100, Study drug stop date + 7 days]

These time windows are defined based on the planned number of days after the date of first administration of study drug. Reasons to base the time windows on the actual treatment start date rather than the randomization date are:

- If first intake of study drug shows a large delay by e.g. more than one week after the date of randomization, a measurement taken four weeks after randomization rather reflects the drug effect after three weeks than after four weeks and thus may underestimate the treatment effect at this visit.
- With large delays of the introduction of study drug after the randomization, the time window for the first on-treatment visit could include times the patient was not yet on study drug.

Proprietary confidential information © 2017 Boehringer Ingelheim International GmbH or one or more of its affiliated companies

Table 6.7: 2

Time windows for on-treatment efficacy measurement scheduled for each on treatment visit

Visit Number	Visit label	Planned days	Time window (actual days on treatment)	
			Start	End ^A
3	Baseline	1	NA	1 ^B
5	Week 4	29	2	57
EOT	Week 12	85	58	Study drug stop date + 7 days

A In case of premature discontinuation of the study drug an EOT Visit has to be performed. If such an EOT Visit falls into the time window of a previous visit, measurements will be assigned to this previous visit and the visit value will be determined as described below. In this case the time window for the visit that includes EOT Visit will end 7 days after the study drug stop date, including Day 7.

B Only values taken prior to the start of treatment with randomized study drug can be considered baseline values. Time windows will be used for assignment of measurements to scheduled visits.

•

Repeated and unscheduled efficacy and safety measurements will be assigned to the nominal visits and listed in the subject data listing (SDL) according to the time windows described above.

If there are several safety laboratory values in one time window on treatment, the worst of these will be selected for the by-visit analyses.

For efficacy measurements, only one observation per time window will be selected for analysis at an on-treatment visit – the value will be selected which is closest to the protocol planned visit day. If there are two observations which have the same difference in days to the planned day or if there are two observations on the same day, the first value will be used. If an observation is available on the last day of treatment, this observation will be preferably selected over any later observation that is still within the time window.

Note: for LOCF imputation, the last observed on-treatment value will be carried forward, whether or not it was selected in the previous time window. For more details on LOCF refer to [section 6.6](#).

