Study-Day (or duration during screening/ run-in)	Duration 1-35 days	Duration at least 14 and at most 21 days after screening period	1	8	15	22	29	57	85	EOT +28
Visit window (in days)				±1	±1	±1	±3	±3	+3	±3
Neuropsychological Rating Scales										
MMSE	X									
FCSRT	X									
Wechsler Memory Paired Associates 	X									
CDR	X									
CDR-SB			X 					X		X
NTB			X 					X		X
MCI-ADSC-ADL			X 							X
ADAS-cog 11	X		X 							X

 Prior to any study related procedure

 Results of a MRI or CCT-scan have to be available before visit 2. Please refer to exclusion #1 ( [section 3.3.3](#) ) for further details.

 The baseline vital signs (supine pulse rate after 5 minutes of rest and systolic/diastolic blood pressure) will be measured before the first dose is taken and at 70-110 minutes post dose. Additional supine pulse rate assessments will be performed at the time points of post-dose PK sampling given in table [10.1.1:1](#) until 70-110 minutes post-dose (See [section 5.2.5.2](#) and [section 6.2](#) for details).

 At all visits, the respective kit number has to be allocated to the patient via IRT

 Only for patients with antidiabetic therapy (see [section 6.2](#) for details).

 Local urine pregnancy test (or blood test if required by local regulations) in women of child bearing potential. More frequent testing may be performed if required by local regulations.

 Columbia Suicide Severity Rating Scale baseline/screening scale

 Columbia Suicide Severity Rating Scale baseline since-last-visit scale

 Also to be completed for patients who are withdrawn or who have discontinued the trial early: in case of early termination visit 7 should be performed no later than 7 days after the last study drug intake (visit FU four weeks later).

 If the assessments at visit 4a do not show clinically relevant findings compared to baseline and if deemed clinically acceptable by the investigator then visits 4b and 4c may be performed as phone contacts. Attendance of the study partner is not necessarily required during visits 4 a-c. ECG and vital signs are only to be performed at clinic visits.

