### 3.3.4 Removal of patients from therapy or assessments

#### 3.3.4.1 Removal of individual patients

An individual patient is to be withdrawn from the trial if:

- The patient withdraws consent, without the need to justify the decision.
- The patient needs to take concomitant drugs that interfere with the investigational product or other study medications(s), refer to [section 4.2.2](#).
- The patient is no longer able to participate for other medical reasons (e.g. surgery, AEs, or other diseases).
- If a patient becomes pregnant during the trial, the investigational drug will be stopped, the patient will be discontinued from the trial and the patient will be followed up until birth or otherwise termination of the pregnancy.
- At visit 3, if the patient experiences sinus tachycardia (defined as resting pulse rate >100 BPM measured in supine position after a minimum of 5 minutes rest) at any time point up to 90±20 minutes post dose or if a pulse rate increase greater than 20 BPM over the pulse rate taken before the first dose administration (baseline) has persisted at 90±20 minutes post-dose. Pulse rate is generally to be measured in a supine position after 5 min rest. See also [section 5.2.5.2](#), and [section 6.2.2](#).
- The patient exhibits serious suicidality, in the clinical judgement of the investigator or according to criteria below:
  - Any suicidal behaviour (i.e. actual attempt, interrupted attempt, aborted attempt, or preparatory acts or behaviour)
  - Any suicidal ideation of type 4 or 5 in the C-SSRS (i.e. active suicidal thought with intent but without specific plan, or active suicidal thought with plan and intent)

A patient can be discontinued after discussion between sponsor and investigator if eligibility criteria have been violated, or if the patient fails to comply with the protocol (e.g. non-attendance at study assessments).

Patients who drop out during screening or during placebo run-in phase prior to randomization (Visit 3) will be considered as screening failure. For patients that screen fail, data will be collected for signed IC, demographics, AE, concomitant medications and randomization and recorded in the eCRFs. No further follow-up is required.

Patients who discontinue or withdraw from the study after randomization (Visit 3) will be considered as “early discontinuations” and the reason for premature discontinuation must be recorded in the eCRFs. The data will be included in the trial database and will be reported.

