6 GENERAL ANALYSIS DEFINITIONS

6.1 TREATMENTS

For regimen details refer to Section 3.1 of the CTP.

The treatments and treatment periods are defined as follows:

Table 6.1: 1 Treatment descriptions

TPATT	Long Name	Short Name
A	BI 409306 10 mg QD	10mg QD
B	BI 409306 25 mg QD	25mg QD
C	BI 409306 50 mg QD	50mg QD
D	BI 409306 25 mg BID	25mg BID
E	Placebo	Placebo

Table 6.1: 2 Definition of analyzing treatment period

Label	Interval	Start Date	Start time
Screening	Screening	Date of informed consent	00:00
Placebo Run-in (PBORI)	Run-in	Date of first administration of run-in medication	Time of first administration of run-in medication 12:00 if missing
BI 409306 10mg QD BI 409306 25mg QD BI 409306 50mg QD BI 409306 25mg BID Placebo	Treatment	Date of first administration of study medication	Time of first administration of study medication 12:00 if missing
Post-treatment	Post-treatment	Date of last intake of study drug + X+1 (see definition of X below)	00:00
Post-study	Post-study	Start date = Last contact date, defined as the maximum of (Trial completion date, last study drug intake + X) +1	00:00

Proprietary confidential information © 2017 Boehringer Ingelheim International GmbH or one or more of its affiliated companies

For safety analyses, data up to 7 days after last treatment intake will be considered as on treatment for AEs and for laboratory values. To clarify;

- Screening: starts from the date of informed consent to the date of first administration of run-in medication.
- Placebo run in period: starts from the date of first administration of run-in medication to the date of first administration of randomized study drug.
- On treatment: From the first intake of randomized study drug to last intake of randomized study drug + X days, where X=7 days for safety laboratory and AE.
- Post-treatment: From end of on-treatment period until last contact. Last contact date is defined in Table 6.1: 1. Post treatment period is not applicable for patients with last contact equal to 'last intake + X + 1 days' where X is 7 days as previously specified.
- Post study: From day after last contact defined in [Table 6.1: 1](#). If period starts at end of on-treatment period then post-treatment period is not applicable.

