7.8.3 Vital signs

Only descriptive statistics are planned for this section of the report.

Proprietary confidential information © 2017 Boehringer Ingelheim International GmbH or one or more of its affiliated companies

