7.8.4 ECG

12-lead ECG measurements will be assessed as described in the CTP Flow Chart. ECG-findings before first intake of study drug will be considered as baseline condition. Any clinically significant new findings in the ECG measurement after the first ECG will be considered as AEs and analyzed as planned in [section 7.8.1](#).

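### SAP 6.7 conflicts with SAP 6.1 and the protocol on vital-sign baseline and Day 1 windows, so the visible by-visit tables would not isolate the acute Visit 3 pulse effect

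*SAP*

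**What the plan says.** **Protocol.** Section 1.2 (Clinical safety) reports a plasma-concentration-dependent rise in supine pulse that peaks 20-30 minutes after dosing and fades quickly. Section 5.2.5.2 adds extra measurements at Visit 3 only: supine pulse pre-dose and at the post-dose PK times up to 90±20 minutes, and orthostatic blood pressure and pulse pre-dose and at 90±20 minutes. The reference value is stated twice. Flow Chart footnote 3: "The baseline vital signs (supine pulse rate after 5 minutes of rest and systolic/diastolic blood pressure) will be measured before the first dose". Section 3.3.4.1 judges the pulse increase "over the pulse rate taken before the first dose administration (baseline", where the last word is the protocol's own label for that reading.

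**SAP baseline rules.** Section 6.7 sets the efficacy baseline at pre-treatment Visit 3 and continues: "All other baseline variables will be observed from Visit 1". Two exceptions are written out. Laboratory, in 6.7: "For laboratory safety measurements, the last values prior to study drug administration will be considered as baseline values". ECG, in 7.8.4: "ECG-findings before first intake of study drug will be considered as baseline condition". Section 7.8.3 on vital signs consists of one sentence: "Only descriptive statistics are planned for this section of the report".

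**SAP windows and periods.** Table 6.7:1, which covers all pre- and on-treatment safety visits, gives Visit 3 (labelled Baseline) the interval [NA, 1] and Week 1 the interval [2, 11]. Section 6.1 defines on-treatment as "From the first intake of randomized study drug to last intake of randomized study drug + X days", and Table 6.1:2 starts that period at the clock time of the first dose.

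**The concern.** The Visit 3 series exists to catch a short-lived pulse effect, so its useful summary is the change from the pre-dose reading to each post-dose reading, by arm. The SAP's visible rules do not produce that summary. The only rule that reaches vital signs points to Visit 1, and the only window that takes the post-dose readings is the one labelled Baseline. A programmer following the text could take change from a screening value, or could put pre-dose and post-dose readings into one row with nothing to say which is used. At stake is whether the report's by-visit vital-sign tables show, by dose arm, the acute effect these readings were added to detect.

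**Working it through.** No sample-size or power figure is involved. The check sets the rules side by side and traces the Visit 3 readings through them.

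1. **Which baseline applies to vital signs?** SAP 6.7 gives Visit 3 for efficacy, the last pre-drug value for laboratory, and Visit 1 for the rest; SAP 7.8.4 gives a pre-intake rule for ECG. Vital signs have no exception, so the literal answer is Visit 1. If the Visit 1 sentence is meant only for baseline characteristics, vital signs have no stated baseline. Neither reading gives the protocol's pre-dose Visit 3 value.

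2. **How far back is Visit 1?** The Flow Chart gives screening 1-35 days and run-in 14-21 days. Shortest gap: 1 + 14 = 15 days. Longest: 35 + 21 = 56 days. The pre-dose Visit 3 reading is taken at the same visit as the dose.

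3. **Where do the post-dose readings fall by window?** Study day = 1 + floor(minutes after dose / 1440). For 20, 30, 70, 90 and 110 minutes the result is Day 1 each time. Visits preferably start before 9:00 AM (Protocol 6.1), so the calendar date does not change either. Under Table 6.7:1, Day 1 belongs to [NA, 1], labelled Baseline; the next row opens on Day 2. The table has no Day 1 post-dose row.

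4. **Where do they fall by period?** Under SAP 6.1 and Table 6.1:2, any reading after the clock time of first intake is on-treatment. The same readings are therefore on-treatment by period and sit in the Baseline row by window.

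5. **Which value is used when several fall in one window?** SAP 6.7 answers for laboratory data (the worst) and efficacy (the closest to the planned day). It gives no answer for vital signs, although Visit 3 generates several Day 1 pulse values by design.

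6. **Does other text settle it?**
   - The footnote to Table 6.7:2 says "Only values taken prior to the start of treatment with randomized study drug can be considered baseline values", but it is attached to the efficacy table. Borrowed for safety, it would bar post-dose readings from being baseline values, yet would still give them no on-treatment row.
   - SAP 7.8 defers to Protocol 7.3.3, which compares vital signs with pre-treatment findings. Visit 1 and pre-dose Visit 3 both fit.

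7. **Can later visits show the effect?** Visits 4a, 5, 6 and EOT have on-treatment windows. However, the home morning dose is withheld on visit days (Protocol 4.1.4), no dose is given at EOT (6.2.2), and the visible text states no post-dose timing for vital signs at these visits. Such readings can miss a peak at 20-30 minutes. Patients who meet the Visit 3 pulse criteria are to be withdrawn (Protocol 3.3.4.1), so the strongest responders would be under-represented in later on-drug readings.

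**The case against.** The strongest reply is that this is a labelling gap in a purely descriptive safety summary of an exploratory trial.

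- Table 6.7:1 itself labels Visit 1 Screening and Visit 3 Baseline, and Protocol 7.3.3 lists screening and baseline as separate occasions, so a Visit 1 baseline was probably not intended. This is plausible, but it makes the SAP contradict itself; it does not supply the missing rule.
- Windows assign readings to visits, and falling in the Visit 3 window does not make a reading a baseline value. No rule pools or averages vital signs. Both statements are correct. They limit the consequence without adding a post-dose time point.
- The readings are on-treatment by period. Clinically relevant vital-sign changes are recorded as AEs (Protocol 5.2.2.1), and AEs leading to discontinuation are tabulated by arm (SAP 7.8.1.3). This stands. But AE reporting depends on the investigator's judgement of relevance, and item E2 in SAP Table 6.2:1 flags patients who were not discontinued; it does not count those who met the criteria.
- Parts of the SAP and the protocol's PK sampling schedule are blacked out, so a separate time-matched pulse analysis cannot be excluded. This also stands, and the point is confined to the visible text. The baseline rule, the windows and 7.8.3 are all legible.

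**Conclusion.** The point holds as an inconsistency with a practical consequence. SAP 6.7 conflicts with the protocol on the vital-sign baseline and with SAP 6.1 on the status of the Day 1 post-dose readings, and 7.8.3 does not resolve either. As written, the visible by-visit tables would not isolate the acute pulse effect.

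A reader might go further in three ways that the documents do not support.

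- **That the effect cannot appear as an on-treatment change.** The readings are on-treatment by period, AE reporting remains, and a redacted analysis is possible.
- **That a rise of about 13 bpm would be hidden.** The 12.9 bpm figure comes from Chinese CYP2C19 poor metabolizers given a single 100 mg dose, twice the largest single dose here (50 mg). The 7-13 bpm median maximum likewise refers to poor metabolizers at 100 mg. These figures say nothing direct about the size of the effect in this trial.
- **That a Visit 1 baseline doubles the SD of change.** Assume a single-reading SD of 6-8 bpm between days and 3-4 bpm within a session (neither figure is in the documents). The SD of change is then √2 × 6-8 = 8.5-11.3 against √2 × 3-4 = 4.2-5.7 bpm. That contrast applies only to same-session Day 1 changes. From Week 1 onward, change from either baseline is between days, so on these assumptions the penalty disappears.

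The conclusion rests on reading the visible SAP text literally. It should be settled before unblinding.

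**What to change.** **SAP 6.7.** (a) Define baseline for vital signs as the last pre-dose Visit 3 value, in line with Protocol 3.3.4.1 and Flow Chart footnote 3. (b) In Table 6.7:1, split Day 1 at the clock time of first randomised intake into Visit 3 pre-dose (baseline) and Visit 3 post-dose (on-treatment, by nominal time), which also brings the table into line with SAP 6.1.

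**SAP 7.8.3.** Tabulate by arm the change in supine pulse from pre-dose at each Visit 3 post-dose time, the maximum change, and the number of patients meeting each existing pulse criterion of Protocol 3.3.4.1. If a redacted section already does this, a cross-reference from 7.8.3 is enough.

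**Cost.** SAP wording and one or two descriptive tables. The data are already collected, and no trial procedure or clinical rule changes.
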